8.3.2 Method of Detecting AEs and SAEs

Individual diary cards, specifically designed for this study by the Sponsor and provided to the study sites, will be given to study participants' parents / legally acceptable representatives for the recording of daily safety information. These diary cards will include pre-listed terms and intensity scales as well as areas for free text to capture additional safety information or other relevant details. Participants' Parents / LARs] will also be provided with standard digital thermometers for measuring daily temperatures. To ensure consistency of reporting, the study sites will instruct participants' parents / LARs on how to correctly use these tools.

At specified intervals, the investigator or a designee will interview the participants' parents / legally acceptable representatives to collect the information recorded in the diary card, and will attempt to clarify anything that is incomplete or unclear. All clinical study information gathered by the study site will be reported electronically by the investigator or designee using a web-based CRF. Any information that was not documented in the diary card will first be captured in the source document and then reported electronically.

The 6-month follow-up should be done at least 180 days after the last vaccination for all participants having received at least one dose of the study intervention, by interviewing participants' parents / legally acceptable representatives either during a visit or over the telephone using a questionnaire to capture SAEs and AESIs, if applicable.

Care will be taken not to introduce bias when detecting AEs and/or SAEs. Open-ended and non-leading verbal questioning of the participant is the preferred method to inquire about AE occurrences.

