### **3.4.6.1.4 Start Date and End Date**

Missing or partially missing start dates or end dates for unsolicited AEs (including SAEs) will remain missing and not be imputed. If the start date is missing or partially missing, the time of onset will be considered to be missing. Nevertheless, unsolicited AEs with missing time of onset will be included in analyses according to the last vaccination (computed according to the [Section 4.2.4.2.3](#)). If either the start date or end date is missing or partially missing, the duration will be considered missing.

Missing or partially missing end dates for ongoing solicited AEs will remain missing and not be imputed.

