##### 4.2.4.2.4 Time of Onset

Time of onset is derived from the start date of the unsolicited AE and the date of last vaccination as described in [Section 4.2.4.2.3](#):

- start date of the unsolicited AE – date of last vaccination before the unsolicited AE

The time of onset is considered as missing only if one or both dates are missing or partially missing.

The unsolicited AEs will be analyzed “within 28 days” after each vaccination (i.e. acute phase), which corresponds to AEs with a time of onset between D01 and D29 days. An AE with missing time of onset will be considered to have occurred just after the last vaccination (computed according to the [Section 4.2.4.2.3](#)), so will be included in these tables.

Time of onset period is displayed as D01-D04, D05-D08, D09-D15, D16 or later, and Missing.

Note: Unsolicited AE that occurred before vaccination (negative time of onset) or with a time of onset higher than defined above will not be included in analysis but will be listed separately

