#### **4.2.4.2.7 Serious Adverse Events**

An event will be considered as a serious event if “Yes” is checked for “Serious” in the eCRF.

SAEs will be analyzed throughout the study using the following periods:

- Within 28 days after any vaccination
- During the study (i.e., all SAEs occurred during the study)

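### An SAE with a partly missing start date is counted in the 28-day SAE table even when its known month and year put it outside that window

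*SAP*

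**What the plan says.** Four SAP rules act in sequence.

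- **Partial dates (SAP 3.4.6.1.4).** "Missing or partially missing start dates or end dates for unsolicited AEs (including SAEs) will remain missing and not be imputed". Further, "If the start date is missing or partially missing, the time of onset will be considered to be missing". Such events are kept: "unsolicited AEs with missing time of onset will be included in analyses according to the last vaccination".
- **Which vaccination (SAP 4.2.4.2.3).** With a partial date, the visit field in the eCRF decides which dose counts as the last vaccination. It has no other role.
- **Placement (SAP 4.2.4.2.4).** "An AE with missing time of onset will be considered to have occurred just after the last vaccination", and it therefore goes into the 28-day tables. The window is the one "which corresponds to AEs with a time of onset between D01 and D29 days". Late events are removed only if they are events "with a time of onset higher than defined above will not be included in analysis but will be listed separately".
- **SAE tables (SAP 3.4.3.2 and 4.2.4.2.7).** SAEs are reported for two periods, the whole study and "Within 28 days after any vaccination". Neither section has a date rule of its own, and SAP 4.2.4.3 adds only worst-case selection across doses.

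On collection, Protocol 8.3.1 limits non-serious unsolicited AEs, MAAEs and AESIs to D01-D29 and D57-D85, but follows SAEs from D01 to 180 days after the last vaccination. Protocol 8.3.2 adds a late contact with the parents: "The 6-month follow-up should be done at least 180 days after the last vaccination".

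**The concern.** Treating an undated event as acute is a sensible default when nothing is known about its timing. Here something is known. A start date with month and year but no day can show that the event fell outside the window, and the SAP discards that information.

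For events collected only inside the windows the default does little harm, because an undated event almost certainly belongs there. SAEs are different: most of their follow-up lies outside the windows, and the last contact is an interview about several months. The questionnaire at that contact also mentions AESIs where applicable, so an AESI reported then could meet the same rule.

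At stake is the accuracy of the 28-day SAE count. In arms of 50, a single late SAE moved into that table is visible.

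**Working it through.** The plan states no figure on this point, so there is none to reproduce. The check traces the rule and then sizes it.

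**1. Tracing the rule.** Illustration: D01 on 21 July 2023 (the randomization cut-off for the first interim analysis in SAP 3.5), dose 2 on schedule, and an SAE recorded as January 2024 with the day unknown.

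- Dose 2 = 21 July + 56 days = 15 September 2023.
- The dose 2 window ends on 15 September + 28 days = 13 October 2023.
- Earliest possible onset is 1 January 2024, which is 15 + 31 + 30 + 31 + 1 = 108 days after dose 2.
- Under 3.4.6.1.4 onset is missing. Under 4.2.4.2.3 the last vaccination is dose 2. Under 4.2.4.2.4 the event is taken as occurring just after dose 2 and enters the 28-day table.
- The exclusion of late events cannot act, because it needs a computed time of onset.

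**2. Follow-up outside the windows.** Inputs: SAE follow-up D01-D237 (D57 + 180 days) and windows D01-D29 and D57-D85 (Schedule of Activities; Protocol 8.3.1).

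- Days inside: 29 + 29 = 58.
- Days outside: 237 - 58 = 179, and 179/237 = 75.5%.
- From dose 2 onward: D57-D237 is 181 days, of which 181 - 29 = 152 (84%) lie outside.

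**3. Days on which the month alone settles the matter.** For each of the 365 possible D01 dates in 2023, I counted the days in D30-D56 whose calendar month contains no day of the dose 1 window, and the days in D86-D237 whose calendar month contains no day of the dose 2 window.

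| Period | Days | Mean days excluded by month |
|---|---|---|
| D30-D56 | 27 | 12.4 |
| D86-D237 | 152 | 137.2 |
| Total | 179 | 149.6 |

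Mean share of follow-up: 149.6/237 = 63%. By start date the total ranges from 123 to 176 days, or 52% to 74%.

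**4. Effect on the table.** Inputs: 50 per arm (SAP 3.2) and two-sided 95% Clopper-Pearson limits (SAP 3.4.1).

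| Children counted | Percentage | 95% limits |
|---|---|---|
| 0/50 | 0% | 0 to 7.1% |
| 1/50 | 2.0% | 0.05 to 10.6% |
| 2/50 | 4.0% | 0.5 to 13.7% |

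For 0/50 the upper limit is 1 - 0.025^(1/50) = 7.1%. For 1/50 it is the 0.975 quantile of Beta(2, 49), 10.6%. The counts of 1 and 2 are illustrative; the documents give no expected number of partly dated SAEs.

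**The case against.** The best defence is that this is a deliberate worst-case convention. It matches other choices in the SAP: a missing causal relationship counts as related (3.4.6.1.2), and results after any vaccination take the worst case (4.2.4.3). The rule can add events to the 28-day table but never remove one, and it applies to both arms. Displays of onset have a missing category, and listings must flag partial dates, so with 100 children a reader could find the case. Partial dates may also be rare: investigators review hospital records for each SAE (Protocol 10.2.3), SAEs are reported within 24 hours of awareness, and a memory aid is provided at D85.

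Most of this stands as a limit on size. It does not justify overriding a recorded month that rules the window out, and neither the listing nor the missing category corrects the 28-day count.

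Three stronger readings are tempting, but the documents do not support them.

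- **That a partly dated SAE has a 76% chance of being misplaced in a way the month would reveal.** The 75.5% is the share of days outside the windows. It includes days whose month overlaps the window, where the month settles nothing; the relevant share averages 63%. Either figure is a probability only if onset is uniform over follow-up.
- **That the miscount reaches Health Authorities through the interim reports.** Those analyses cover D01-D22 (Protocol 9.4; SAP 3.5), so a later SAE cannot be in them.
- **That every partly dated SAE is affected.** An SAE placed before dose 1 by its visit field has no last vaccination to be assigned to.

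**Conclusion.** The point holds as a narrow defect in a derivation rule. On the SAP's own wording, a post-vaccination SAE with a partly missing start date is counted as acute even when its known month and year exclude that, and no other section prevents it.

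Its consequence is modest: 2 percentage points per affected child in an arm of 50, in one descriptive table of the final analysis, with no hypothesis tested. The protocol's SAE endpoint is the presence of SAEs throughout the study, and that count does not change. A reader might infer that a false imbalance between arms is likely. The documents do not support that, because the frequency of partial dates is not given and is probably low.

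The sizes assume the planned visit days, 50 treated children per arm and, for the 52 to 74% range, D01 dates spread over the 2023 calendar. The case for changing the rule rests on its being wrong when it applies and on the low cost of repair.

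**What to change.** In SAP 3.4.6.1.4 and 4.2.4.2.4, keep the worst-case placement only when the known part of the start date leaves onset within 28 days of the last vaccination possible. Otherwise:

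- if the earliest possible date is more than 28 days after the last vaccination, leave the event out of the 28-day table and report it in the whole-study SAE table;
- if the latest possible date is before the first vaccination, leave it out of the 28-day table and put it in the pre-vaccination listing.

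Events with no usable date information stay under the present rule, so the conservative intent is kept. The cost is one SAP sentence and a small programming step that derives the earliest and latest possible dates. It needs no new data and can be set before database lock without reference to results by arm.

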#### **4.2.4.2.5 Duration**

Duration is derived from the start and end dates of the unsolicited AE:

- end date of unsolicited AE – start date of unsolicited AE + 1.

The duration is considered as missing only if one or both of the start and end dates of the unsolicited AE is missing or partially missing.

Duration period is displayed as 1-3 days, 4-7 days, 8-14 days, 15 or more, and Missing

#### **4.2.4.2.6 Medically-Attended Adverse Event**

An event will be considered as an MAAE if “Yes” is checked for “Is the event an MAAE?” in the eCRF.

#### **4.2.4.2.7 Serious Adverse Events**

An event will be considered as a serious event if “Yes” is checked for “Serious” in the eCRF.

SAEs will be analyzed throughout the study using the following periods:

- Within 28 days after any vaccination
- During the study (i.e., all SAEs occurred during the study)

#### **4.2.4.2.8 Adverse Events of Special Interest**

An event will be considered as an AESI if “Yes” is checked for “Is the event an AESI?” in the eCRF.

The following AESIs will be assessed during the Acute Phases of the study:

#### **4.2.4.3 Solicited and Unsolicited AEs after any vaccination**

This section is applicable for tables which present results after any vaccination.

The rules for calculation are to select the worst case:

- Maximum intensity: Select the maximum overall intensity for any vaccination
- Time of onset: Select the minimum time of onset for any vaccination
- Duration (for unsolicited AE): Select the maximum duration for any vaccination

## 4.2.5 Other Safety Endpoints

### 4.2.5.1 Pregnancy

Not applicable as women of childbearing age will not receive the study intervention.

### 4.2.5.2 Action Taken

Missing actions taken will remain missing and will not be imputed

### 4.2.5.3 Seriousness

This information will be summarized as collected. No derivation or imputation will be done.

### 4.2.5.4 Outcome

This information will be summarized as collected. No derivation or imputation will be done.

### 4.2.5.5 Causal Relationship

This information will be summarized as collected in the field “Relationship to study vaccine”. Missing causal relationship will be handled as described in [3.4.6.1.2](#). Relationship to study procedure is only presented in the listing.

### 4.2.5.6 Adverse Events Leading to Study Discontinuation

A flag is available in the clinical database for all AEs in order to identify AEs leading to study discontinuation.

The items that are counted are:

- Disposition table: A subject who, on the “Completion at End of Study” form question “What was the subject's status?” has “Adverse Event” checked.
- Safety overview table: A participant who has either on the “Completion at End of Study” form question “What was the subject's status?” has “Adverse Event” checked, or lists a solicited AE that has “Caused Study Termination” checked that is at least Grade 1 or an unsolicited AE that has “Caused Study Discontinuation” checked that is at least Grade 1 or missing and is within the time period indicated.
- System Organ Class (SOC)/Preferred Term (PT) table: A solicited AE that has “Caused Study Termination” checked that is at least Grade 1 or an unsolicited AE that has “Caused Study Discontinuation” checked that is at least Grade 1 or missing and is within the time period indicated.

## 4.2.6 Immunogenicity

### 4.2.6.1 Computed Values for Analysis

In order to appropriately manage extreme values (< lower limit of quantification [LLOQ] and  $\geq$  upper limit of quantification [ULOQ]) for analysis purposes, the following computational rule is applied to the values provided in the clinical database for each blood sample drawn:

- If a value is < LLOQ, then use the computed value LLOQ/2
- If a value is between  $\geq$  LLOQ and < ULOQ, then use the value
- If a value is  $\geq$  ULOQ, then use the computed value ULOQ

For the RSV serum anti-F IgA antibodies, we will consider the LOD value for the calculation instead of the LLOQ.

Note for titers converted into IU/mL:

The IU/mL is computed using the following calibration formulae:

$$\text{IU/mL} = \frac{\text{Sample Titer}}{(\text{Assay calibrator})/\text{Assigned Potency}} = \frac{\text{Sample Titer}}{(\text{Assay calibrator})/\text{Assigned Potency}}$$

Where:

- *Sample Titer*: This is the titer directly observed from the sample using one plate.
- *Assigned Potency*: The established internal reference standard and replacement for International
- *Assay calibrator*: Each plate will also measure the titer of the reference standard

Because of this calibration formula, LLOQ related to titers can be calibrated to different IU/mL depending on the observed titer of calibrator (international reference or in-house reference); so titer < LLOQ is not consistent converting to IU/mL from run to run.

As a consequence, for any value reported as “< X”, we use the computed value X/2. No ULOQ is defined.

### 4.2.6.2 Fold-rise

For calculation of fold-rise and geometric mean titer ratio (GMTR) a titer reported as < LLOQ will be converted to  $\frac{1}{2}$  LLOQ for a numerator and will be converted to LLOQ for a denominator. If both numerator and denominator are < LLOQ, then both will be converted in the same way so that titer ratio=1. This rule is used to minimize the numerator and maximize the denominator as a conservative approach. For the RSV serum anti-F IgA antibodies, we will consider the LOD value for the calculation instead of the LLOQ.

Note for titers converted into IU/mL: This rule would apply using X instead of LLOQ

If the computed value is  $\geq$  4-fold rise, then the derived  $\geq$  4-fold rise indicator will be “Yes” for that test, otherwise  $\geq$  4-fold rises will be “No”.

Note: If either numerator or denominator is missing, then fold-rise computed value/indicator is missing.

#### 4.2.6.3 Baseline RSV serostatus

For this Sanofi Phase II study, baseline RSV serostatus will be determined from serum samples collected at baseline (V01). Participants will be categorized into RSV-exposed or RSV-naïve based on the presence or absence of detectable serum anti-F IgA antibodies. This biomarker has been chosen since it is produced only in response to RSV infection and not transferred transplacentally from mother to child. Baseline serostatus will be determined as follows:

- ***RSV-naive*** for participants with baseline IgA titer < LOD
- ***RSV-exposed*** for participants with baseline IgA titer  $\geq$  LOD
- ***Undetermined*** for participants with baseline IgA titer ‘missing’ or ‘NR’.

#### 4.2.7

#### 4.2.7.1

## **4.2.8 Derived Other Variables**

### **4.2.8.1 Age for Demographics**

Calendar age (in months) calculated using date of birth collected at time of visit 01 will be used in the analysis.

Following age groups will be derived, corresponding to stratification factor:

- < 12 months: until the last day before the 1st birthday date
- $\geq$  12 months: from 1st birthday date

### **4.2.8.2 Duration of a Participation in the Study**

The duration of a participation in the study is computed in days as follows: maximum (date of visit, date of termination form, 6-month follow-up contact) - date of visit 01 +1.

### **4.2.8.3 Duration of the Study**

The duration of the study is computed in days as follows: maximum of all participants (date of visit, date of termination form, 6-month follow-up contact) - minimum for all participants (date of visit 01) +1.

### **4.2.8.4 Duration of a Participation in the Study Intervention Phase**

The duration of a participation in the study is computed in days as follows: maximum (date of visit, date of termination form) - date of visit 01 +1.

### **4.2.8.5 Duration of the Study Intervention Phase**

The duration of the study is computed in days as follows: maximum of all participants (date of visit, date of termination form) - minimum for all participants (date of visit 01) +1.

## 5 Changes in the Conduct of the Trial or Planned Analyses

Not applicable

## 6 Supporting Documentation

### 6.1 Appendix 1 List of Abbreviations

AE	Adverse Events
AESI	Adverse events of special interest
AR	Adverse reactions
ARI	Acute respiratory illness
CRF	Case report form
DMC	Data Monitoring Committee
ELISA	Enzyme-linked Immuno-adsorbant Assay
FAS	Full analysis set
GCI	Global Clinical Immunology
GCP	Good Clinical Practice
GM	Geometric mean
GMT	Geometric mean of titer
GMC	Geometric mean of concentration
ICH	International Council for Harmonisation
IMP	Investigational Medicinal Product
LAR	Legally acceptable representative
LRI	Lower respiratory tract illness
LOD	Limit of detection
LLOQ	Lower level of quantitation
MAAE	Medically attended adverse event
MedDRA	Medical Dictionary for Regulatory Activities
NA	Not applicable
NC	Not computed
NIMP	Non- Investigational Medicinal Product
PPAS	Per-protocol analysis set
RCDC	Reverse cumulative distribution curve
RSV	Respiratory Syncytial Virus
SAE	Serious adverse events
SafAS	Safety analysis set

---

SAP	Statistical analysis plan
SOC	(Primary) System organ class
PT	Preferred term
TLF	Tables, listings and figures
ULOQ	Upper level of quantitation
URI	Upper respiratory tract illness

## 6.2 Appendix 2 Use the Reed-Frost models and Greenwood models to estimate the transmission probability.

The binomial model is often used to estimate the transmission probability based on the idea that exposure to infection occurs in discrete contacts. Generally,  $p$  is defined as the transmission probability during a contact between a susceptible person and an infectious person. The quantity  $q = 1 - p$  is the probability that the susceptible person will not be infected during the contact, called the escape probability. In this section, the susceptible person is considered the pediatric participant who received placebo, and an infectious person is considered the pediatric participant who received RSVt vaccine.

Chain binomial models are dynamic models developed from the simple binomial model by assuming that infection spreads from individual to individual in populations in discrete units of time, producing chains of infection governed by the binomial probability distribution. The Reed-Frost and Greenwood models are examples of chain binomial models. To use these models, the number of susceptible persons and the number of infectious persons involved in each transmission generation should be known. However, in this study, the actual transmission chains is not observed, thus a single transmission generation is considered.

A contact group is defined as a group of pediatric participants who live in the same household or who attend in the same daycare center. A contact group is considered as a transmission unit and different contact groups are assumed to be separate and independent of one another. A total of  $J$  contact groups is assumed.  $S_j$  and  $I_j$  are the number of pediatric participants who received placebo and the number of pediatric participants who received RSVt vaccine in the  $j$ th contact group, respectively.  $X_j$  is the total number of pediatric participants who received placebo and have detective vaccine virus in the  $j$ th contact group.

